14.3. Interim Analysis

One of two interim analyses may be performed. Retrotope will determine which interim, if either, to perform.

Interim analysis 1 using Month 4 data.

An interim analysis may be performed when all subjects have completed the Month 4 visit.

The Interim Analysis Committee (IAC) will report the following information to the steering committee, which will report the information to Retrotope management.

- The average within-treatment-group standard deviation of the change from baseline to Month 4 in CPET
- The average within-treatment-group standard deviation of the change from baseline to Month 4 in mFARS

That is, for CPET and for mFARS, the IAC statistician will calculate the within-treatment-group standard deviation of the change from baseline to Month 4 for each treatment group, and then calculate the average of the standard deviations of the two treatment groups.

The IAC will not report the mean change from baseline within treatment group and will not report the difference between the treatment groups in the mean change from baseline.

Retrotope may use this information on average within-treatment-group standard deviation to consider stopping the trial for futility or to consider sample size re-estimation.

The Interim Analysis Committee (IAC) will report the Pearson and Spearman correlation of the change in CPET with the change in mFARS at 4 months, and at the last available time point for each subject. Retrotope may use this information to re-order the primary and first secondary analyses.

There will be no alpha penalty for this interim analysis for the following reasons.

- 1. Only the average within-treatment-group standard deviations will be reported.
- 2. Neither mean change from baseline within treatment group nor the difference between the treatment groups in the mean change from baseline will be reported to Retrotope.
- 3. Retrotope will remain blinded to treatment assignments.

Interim analysis 2 using Month 11 data.

An interim analysis may be performed when approximately half the subjects have completed the Month 11 visit.

The Interim Analysis Committee (IAC) will report the following information to the steering committee, which will report the information to Retrotope management.

- The results of a futility analysis for the CPET endpoint
- The results of a futility analysis for the mFARS endpoint

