Retrotope may use this information to consider stopping the trial for futility, to change the order of the primary and secondary endpoint, or to consider sample size re-estimation.

The Interim Analysis Committee (IAC) will report the Pearson and Spearman correlation of the change in CPET with the change in mFARS at 4 months, and at the last available time point for each subject. Retrotope may use this information to re-order the primary and first secondary analyses.

There will be no alpha penalty for this interim analysis for the following reasons.

1. The trial cannot be stopped for efficacy at this interim. It can only be stopped for futility.

Retrotope will remain blinded to treatment assignments.

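### Interim 2 may change which endpoint is primary on the strength of futility results, but the reasons given for no alpha adjustment cover futility stopping only

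*Combined protocol and SAP*

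**What the plan says.** Section 14.3 offers two interim analyses, at most one of which will be run: "Retrotope will determine which interim, if either, to perform". The second takes place when about half the subjects have completed Month 11. The interim committee reports two items through the steering committee to sponsor management: "The results of a futility analysis for the CPET endpoint" and "The results of a futility analysis for the mFARS endpoint". On their use, the section says: "Retrotope may use this information to consider stopping the trial for futility, to change the order of the primary and secondary endpoint". Sample size re-estimation is a third permitted use.

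The section continues: "There will be no alpha penalty for this interim analysis for the following reasons". The first reason is "The trial cannot be stopped for efficacy at this interim. It can only be stopped for futility". A second statement follows: "Retrotope will remain blinded to treatment assignments".

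Interim 1 makes the same claim about alpha, but there the committee "will not report the difference between the treatment groups in the mean change from baseline". Interim 2 contains no such restriction.

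Section 7 makes MVO2 the primary endpoint and the GST the key secondary, and lists mFARS as exploratory. Section 14.2 sets alpha at two-sided 0.05. Section 14.1 defers full methods to a separate statistical analysis plan, to be final before unblinding and statistical analysis. That plan is not among the documents.

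**The concern.** The plan allows three uses of the futility results and justifies one. Ruling out an efficacy stop explains why a look that can only end the trial for futility costs no alpha. It does not address a look that can decide which hypothesis is tested as primary.

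Blinding to subject-level assignments does not close the gap. A futility result for an endpoint reflects the comparison between arms, so two such results tell management which endpoint is doing better. The subjects behind them stay in the final test, and a promoted endpoint therefore carries forward its favourable first half. Interim 1 can rely on no treatment difference being reported; interim 2 cannot.

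At stake is the error rate of the primary claim in a Phase 2/3 efficacy trial. Once management has seen the results and re-ordered the endpoints, the selection cannot be undone.

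**Working it through.** **The plan's own figure.** 30 per arm, difference 15.8, SD 11.1, two-sided 0.05 (Section 14.2): t-test power is 0.9997, which agrees with the stated value of over 99%. It concerns peak workload and does not bear on the interim.

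**Inputs.** From the documents: two-sided 0.05, so 0.025 on the benefit side; 30 per arm; interim at about half the subjects. Assumed: information fraction 0.5; correlation between the two endpoints' test statistics from 0 to 0.9; and a pass/fail rule, in which the second endpoint replaces the primary when the primary's interim z is below a cut k and the second's is above it. Cuts k = 0, 0.5 and 1 correspond to conditional power under the current trend, Φ((k/√0.5 − 1.96)/√0.5), of 0.3%, 4% and 22%.

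**Model.** Under the null, each endpoint's final statistic is Z = (z1 + z2)/√2, with z1 from the first half of the information and z2 from the second. False benefit means that the endpoint finally tested has Z > 1.96.

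**Step 1: futility stopping only.** Stopping when z1 < 0 leaves P(Z > 1.96 and z1 > 0) = 0.0247. This is no more than 0.025, so the plan's reason is right for this use.

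**Step 2: pass/fail swap at correlation 0, by hand.** Let p(k) = P(Z > 1.96 and z1 > k).
- The original endpoint is kept unless it fails and the other passes. It contributes 0.025 − (0.025 − p)(1 − Φ(k)).
- The promoted endpoint contributes p·Φ(k).
- The sum is p + 0.025·Φ(k).

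| k | p(k) | 0.025·Φ(k) | False benefit |
|---|---|---|---|
| 0 | 0.0247 | 0.0125 | 0.037 |
| 0.5 | 0.0235 | 0.0173 | 0.041 |
| 1 | 0.0202 | 0.0210 | 0.041 |

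**Step 3: other correlations.** Simulation, 4,000,000 null trials per correlation, range over the three cuts:

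| Correlation | Trial continues if both fail | Trial stops if both fail |
|---|---|---|
| 0 | 0.037–0.041 | 0.037–0.040 |
| 0.5 | 0.030–0.035 | 0.029–0.032 |
| 0.9 | 0.025–0.027 | 0.023–0.025 |

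A check with t-tests at 15 per arm (interim) and 30 per arm (final) gave, with continuation, 0.037–0.041, 0.030–0.035 and 0.0256–0.0273.

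**Step 4: two-sided total under the same rule.** With continuation it is 0.050 at cut 0. At cuts 0.5 to 1 it is 0.058–0.062 (correlation 0), 0.056–0.059 (0.5) and 0.051–0.052 (0.9). If the trial stops when both fail, it is 0.023–0.040 at those cuts.

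**Step 5: the literal key secondary.** MVO2 swapped with an equally weighted GST, decided on CPET and mFARS pass/fail results, gives 0.026–0.032 over the correlations tried.

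**Step 6: the other adaptations.**
- Re-sizing one endpoint with the unadjusted test gives 0.0235–0.0248 under promising-zone rules, and 0.031 in the worst case with a twofold cap.
- Re-ordering on the pooled interim correlation alone gives 0.0248–0.0255, which is no inflation.

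**The case against.** **The excess may be negligible.** At correlation 0.9 with stopping when both endpoints fail, there is no material inflation. Correlation 0 is the least plausible case, because Section 6.4 reports cross-sectional correlation among related measures. This stands. A reader might infer that any swap must inflate the error; the documents do not support that, since they give neither the rule nor the correlation.

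**Alpha is stated only as two-sided 0.05.** This is correct, and a reader might infer that the two-sided rate is always breached. Under the pass/fail rule that needs a cut above z = 0 and a trial that continues after both endpoints fail. The benefit side is still the relevant yardstick for an efficacy claim, because there the swap can move error from the harm side to the benefit side without changing the total.

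**mFARS is exploratory, so the swap may mean MVO2 with the GST.** The text does not settle this. Reporting an mFARS futility result makes promotion of mFARS plausible. On the literal reading the excess is smaller.

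**The separate analysis plan may contain the rules.** It may, and an interim comparison can fairly be read as a statistical analysis that must follow its finalization. It therefore cannot be said that no rule will exist before interim 2. Even so, a rule in that plan would leave the protocol's stated justification uncorrected.

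**The information fraction is fixed at 0.5.** The final repeated-measures model also uses earlier visits, so the true fraction may differ. The figures are illustrative to that extent.

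**Conclusion.** The point holds, and should be corrected before interim 2 is run. The statement that no alpha adjustment is needed is justified for futility stopping and unsupported for re-ordering endpoints on the futility results.

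The size is conditional on interim 2 being run, on the order being changed on those results, and on the assumed rule, correlation and information fraction of 0.5. On that basis the chance of a false claim of benefit runs from no material excess to about 0.041 against 0.025. It is 0.026–0.032 if the swap is MVO2 with the GST.

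Three wider readings are not supported:
- The text does not say that the sponsor sees subject-level assignments; it says the opposite.
- Sample size re-estimation does not necessarily inflate error. The gap there is a missing rule and cap.
- Re-ordering on the pooled CPET–mFARS correlation alone showed no inflation and lies outside this point.

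Whether the CPET endpoint means MVO2 or peak workload is a separate matter.

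**What to change.** Choose one package.

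**A (preferred).** Remove endpoint re-ordering from the permitted uses of the interim 2 futility results. Have the committee return only continue or stop for the named primary endpoint. Limit the no-adjustment statement to futility stopping. This is a wording change with no power cost; the sponsor gives up the swap.

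**B.** Keep the swap, but before interim 2 name the candidate endpoints and the swap rule. Test at 0.05 divided by the number of candidates, or use a closed combination test. Two-sided 0.025 each is enough only for exactly two candidates: if the endpoint with the best interim result is chosen, that level gives false benefit of 0.033 with three candidates and 0.041 with four, at correlation 0.

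The cost of B with two candidates is power. At 30 per arm, an effect with 80% power at two-sided 0.05 has about 71% at 0.025 (37 per arm restores 80%), and 90% becomes 84% (36 per arm restores 90%). The documents give no planning effect for MVO2, the GST or mFARS, so the actual loss for them is unknown.

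Under either package, the no-adjustment statement should not extend to sample size re-estimation unless its rule and cap are fixed before interim 2 and shown to control error. Some promising-zone rules meet that test.

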14.4. Deviation from Original Analysis Plan

Deviations from the original statistical or PK analysis plans will be provided in the final clinical study report (CSR).

15. ADVERSE EVENTS

All subjects in the study will have FRDA and the Investigators will take the subjects' Baseline status into account when reporting AEs. Investigators will also consider the underlying disease when designating relationship of AE to study drug, and if AEs are due to the FRDA disease, disease progression or symptomatology exacerbation. Common characteristics of FRDA and RT001 treatment include the following:

- loss of coordination (ataxia) in the arms and legs
- loss of mobility
- fatigue energy deprivation and muscle loss
- vision impairment, hearing loss, and slurred speech
- severe scoliosis
- foot deformities such as clubfoot, flexion of the toes, hammer toes, foot inversion
- diabetes mellitus (insulin-dependent, in most cases)
- hypertrophic cardiomyopathy
- chest pain, shortness of breath, and heart palpitations
- myocardial fibrosis
- heart rhythm abnormalities
- steatorrhea, diarrhea, loose stools

All adverse physical findings/laboratory results identified prior to initiation of study drug will be reported on the medical history and/or physical examination CRFs. After initiation of study drug, any clinically significant changes in physical findings/laboratory results or any new adverse physical findings/laboratory results will be reported as AEs.

15.1. Adverse Event Definitions

15.1.1. Adverse Event

An AE means any untoward medical occurrence associated with the use of a drug in humans, whether or not considered drug related. An AE (also referred to as an adverse experience) can be any unfavorable and unintended sign (e.g., an abnormal laboratory finding), symptom, or disease temporally associated with the use of a drug and does not imply any judgment about causality.

15.1.2. Suspected Adverse Reaction

A suspected adverse reaction means any AE for which there is a reasonable possibility that the drug caused the AE. For the purposes of Investigational New Drug (IND) safety reporting, "reasonable possibility" means there is evidence to suggest a causal relationship between the

drug and the AE. Suspected adverse reaction implies a lesser degree of certainty about causality than adverse reaction, which means any AE caused by a drug.

15.1.3. Life-Threatening Adverse Event or Life-Threatening Suspected Adverse Reaction

An AE or suspected adverse reaction is considered "life-threatening" if, in the view of either the Investigator or Sponsor, its occurrence places the subject at immediate risk of death. It does not include an AE or suspected adverse reaction that, had it occurred in a more severe form, might have caused death.

15.1.4. Serious Adverse Event or Serious Suspected Adverse Reaction

An AE or suspected adverse reaction is considered "serious" if, in the view of either the Investigator or Sponsor, it results in any of the following outcomes:

- Death
- A life-threatening AE see definition above
- Inpatient hospitalization or prolongation of existing hospitalization
- A persistent or significant incapacity or substantial disruption of the ability to conduct normal life functions
- A congenital anomaly/birth defect

Important medical events that may not result in death, be life-threatening, or require hospitalization may be considered serious when, based upon appropriate medical judgment, they may jeopardize the subject and may require medical or surgical intervention to prevent one of the outcomes listed in this definition. Examples of such medical events include allergic bronchospasm requiring intensive treatment in an emergency room or at home, blood dyscrasias or convulsions that do not result in inpatient hospitalization, or the development of drug dependency or drug abuse.

15.1.5. Unexpected Adverse Event or Unexpected Suspected Adverse Reaction

An AE or suspected adverse reaction is considered "unexpected" if it is not listed in the Investigator Brochure or is not listed at the specificity or severity that has been observed.

For example, under this definition, hepatic necrosis would be unexpected (by virtue of greater severity) if the Investigator Brochure referred only to elevated hepatic enzymes or hepatitis. Similarly, cerebral thromboembolism and cerebral vasculitis would be unexpected (by virtue of greater specificity) if the Investigator Brochure listed only cerebral vascular accidents.

"Unexpected," as used in this definition, also refers to AEs or suspected adverse reactions that are mentioned in the Investigator Brochure as occurring with a class of drugs or as anticipated

from the pharmacological properties of the drug but are not specifically mentioned as occurring with the particular drug under investigation.

15.2. Adverse Event Classification

15.2.1. Relationship to Investigational Drug

The Investigator's assessment of causality must be provided for all AEs (serious and non-serious). An Investigator's causality assessment is the determination of whether or not there exists a reasonable possibility that the study drug caused or contributed to an AE, as described below:

- None: No relationship between the experience and the administration of study drug; related to other etiologies such as concomitant medications or subject's clinical state.
- Unlikely: The current state of knowledge indicates that a relationship is unlikely.
- **Possible:** A reaction that follows a plausible temporal sequence from administration of the study drug and follows a known response pattern to the suspected study drug. The reaction might have been produced by the subject's clinical state or other modes of therapy administered to the subject, but this is not known for sure.
- **Probable:** A reaction that follows a plausible temporal sequence from administration of the study drug and follows a known response pattern to the suspected study drug. The reaction cannot be reasonably explained by the known characteristics of the subject's clinical state or other modes of therapy administered to the subject.
- **Definite:** A reaction that follows a plausible temporal sequence from administration of the study drug and follows a known response pattern to the suspected study drug and can be confirmed with a positive re-challenge test or supporting laboratory data.

As this is a blinded study, it is assumed the event is related to the active study drug until proven otherwise.

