15.4. Monitoring of Adverse Event Data

The Investigator and the Sponsor or its representative will be responsible for the following:

- Reviewing AE data on an ongoing basis throughout the study. Should any AE report
 suggest that an unexpected Grade 3 or higher, and probably or definite study drugrelated occur, the Investigator and Sponsor will take prompt and appropriate action to
 protect subject safety. These actions may range from no action (proceed with the
 study) to halting the study for safety reasons. The evaluation and action decided upon
 will be documented.
- Assessing the safety data and providing recommendations if the Sponsor should stop or modify the study.

See Section 8.4 for additional details.

^b Self-care activities of daily life refer to bathing, dressing and undressing, feeding self, using the toilet, taking medications, and not bedridden.

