For SAEs, a Serious Adverse Event Form must also be completed with as much information as possible and submitted in the time frame described below in Section 15.6. When new significant information is obtained as well as when the outcome of an event become known, the Investigator should record the information on a new Serious Adverse Event Form, indicating that it is a follow-up report. If the subject was hospitalized, a copy of the discharge summary and any other relevant hospital records (e.g., admission report, laboratory test results) must be included as part of the subject medical file.

All AEs considered to be related (definitely, probably, or possibly related) to study drug and all SAEs will be followed until resolved or until a stable status has been achieved.

15.6. Notification about Serious Adverse Events and Serious and Unexpected Suspected Adverse Reactions

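### Possible, Probable and Definite all require a known response pattern, so a new type of reaction fits no causality grade and does not meet the Section 15.4 trigger as written

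*Combined protocol and SAP*

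**What the plan says.** Section 15.2.1 asks the investigator to determine "whether or not there exists a reasonable possibility that the study drug caused or contributed to an AE, as described below". Five grades follow. Possible, Probable and Definite open with the same two-part condition, joined by 'and': the reaction "follows a plausible temporal sequence from administration of the study drug and follows a known response pattern to the suspected study drug". They differ only in what comes next, namely whether another cause might explain the event and whether re-challenge or laboratory data confirm it. Unlikely has a different test: "The current state of knowledge indicates that a relationship is unlikely". The section closes by presuming, because the study is blinded, that an event is related to active drug unless shown not to be.

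Section 15.1.2 sets the governing standard: "A suspected adverse reaction means any AE for which there is a reasonable possibility that the drug caused the AE". It adds that reasonable possibility "means there is evidence to suggest a causal relationship between the" drug and the event. It says nothing about a response pattern.

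Section 15.4 calls for prompt action should a report "suggest that an unexpected Grade 3 or higher, and probably or definite study drugrelated occur". Section 15.5 lists the grades that count as related and ties follow-up to them: "All AEs considered to be related (definitely, probably, or possibly related) to study drug and all SAEs will be followed until resolved".

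**The concern.** The grading scale is stricter than the question it is meant to answer. Section 15.2.1 asks about reasonable possibility, then describes grades that cannot be reached without a feature that Section 15.1.2 does not require. The missing feature, a known pattern, is the one that a new kind of reaction lacks by definition.

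Three uses of the grade are at stake. Section 14.1 presents adverse events by relationship to study drug. Sections 15.5 and 9.3.2 tie some follow-up to relatedness. Section 15.4 reserves its prompt-action step for events that are both unexpected and at least Probable, so the grade definition narrows a trigger intended for unexpected events.

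**Working it through.** No arithmetic applies; the check is to apply the definitions to a test event. Take an adverse event with plausible timing, no known response pattern, no evident alternative cause, severity Grade 3, not serious, and not listed in the Investigator Brochure.

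**Step 1: the grades in Section 15.2.1.**

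| Grade | What it requires | Test event |
|---|---|---|
| None | No relationship; other causes account for it | Not met |
| Unlikely | Knowledge pointing against a relationship | Not met: nothing known need point either way |
| Possible | Timing and known pattern | Fails on pattern |
| Probable | Timing and known pattern; disease or other therapy not a reasonable explanation | Fails on pattern |
| Definite | Timing and known pattern; positive re-challenge or supporting laboratory data | Fails on pattern |

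Read strictly, no grade fits. An investigator must still enter one, because the section requires a causality assessment for every event.

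**Step 2: the standard in Section 15.1.2.** Good timing with no competing explanation can be evidence suggesting causation. The same event can therefore be a suspected adverse reaction under 15.1.2 and miss every related grade under 15.2.1, although 15.2.1 presents its grades as the way to decide the 15.1.2 question.

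**Step 3: the presumption sentence.** It says the event is taken to be related but assigns no grade and does not waive the pattern condition. One site may follow the grade definitions and enter Unlikely as the nearest available grade. Another may follow the presumption and enter Possible. Both can point to the text.

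**Step 4: the Section 15.4 trigger.** It needs three things together: unexpected, Grade 3 or higher, and Probable or Definite. The test event meets the first two. On the grade definitions it fails the third. On the generous reading of the presumption it becomes related, which under Section 15.5 means Possible or higher; nothing lifts it above Possible, so it still fails.

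**Step 5: what can still meet the trigger.** Section 15.1.5 counts an event as unexpected if it is unlisted, if it is more severe or more specific than listed, or if it is anticipated from the drug class or pharmacology but not reported with this drug. The last two kinds can follow a known pattern and so can reach Probable or Definite. The gap is confined to reactions of a new type.

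**Step 6: follow-up.** Sections 8.1 and 13.10 follow any event ongoing at the end-of-treatment call, whatever its grade. The related-event rules therefore matter mostly elsewhere: for a subject withdrawn because of an adverse event (Section 9.3.2), and for a non-serious event that begins after that call but within the 90-day reporting period of Section 15.5.

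**The case against.** The strongest case on the other side is that little depends on the grade. Section 15.6.1 requires every SAE to be reported irrespective of causality and lets the Medical Monitor revise relatedness upward but not downward. Many Grade 3 events would be serious, since Section 15.2.2 names hospitalization among the Grade 3 features. Section 15.4 itself requires continuing review of adverse event data and recommendations on stopping or modifying the study, neither tied to relatedness, and its triggered response may be to take no action. A DSMB is planned (8.4.3), and Section 9.3.5 allows the study to be halted at any time for safety. Section 14.1 also tabulates all treatment-emergent events regardless of grade. All of this stands, and it limits the effect. It does not correct the scale: the upward-revision rule sits in the SAE section, and the only causality scale in the protocol is the one in 15.2.1.

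The phrase 'known response pattern' is also undefined. It could be read broadly, to include experience with linoleic acid or other deuterated fatty acids. That reduces the set of affected events but does not empty it.

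Four stronger readings are tempting, and the documents do not support them.

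- A reader might infer that new toxicities will be scored as unrelated across the board. Unlikely does not properly fit them, and the presumption pulls the other way; the supported conclusion is inconsistent grading.
- A reader might infer that expedited reporting fails. Section 15.6.2 turns on a serious and unexpected suspected adverse reaction, which 15.1.2 defines without reference to a grade.
- A reader might take the Section 15 list, which includes steatorrhea and diarrhea, as telling investigators to attribute these to the disease. Its heading is "Common characteristics of FRDA and RT001 treatment include the following", so it names both sources.
- A reader might use the small prior exposure to RT001 to put a figure on the problem. That would bound how common an unseen reaction could be, and would say nothing about how many events would be misgraded.

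**Conclusion.** The concern holds as an internal conflict between Sections 15.2.1, 15.1.2 and 15.4. Under the definitions as written, a plausibly timed reaction of a new type meets no related grade, has no proper home in Unlikely, may be graded differently by different sites, and does not meet the Section 15.4 trigger even if presumed Possible.

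The size is qualitative. The effect falls mainly on non-serious Grade 3 events, on the relationship tables, and on the part of follow-up that depends on relatedness. The conclusion assumes that the two-part condition is applied literally and that 'known' means already recognized, whether for RT001 itself or from its class or pharmacology. Discretion by the investigator or Medical Monitor could produce a different grade in practice, but the text does not provide for it outside the SAE section. This should be fixed; given the safeguards that do not depend on the grade, it is not critical to the trial.

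**What to change.** Align Section 15.2.1 with Section 15.1.2:

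- Remove the known-pattern condition from Possible.
- In Probable and Definite, make a known pattern a supporting feature and not a requirement.
- Replace the closing presumption with an instruction to assess causality as if the subject had received RT001, using the grades above it.
- Reconcile Section 15.4 with the revised grades, so that the sponsor states which grades its trigger is meant to cover, including for reactions of a new type.

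The cost is a wording amendment to the protocol and safety forms and a memo to sites. Slightly more events will be graded Possible, with somewhat more follow-up under Section 15.5. Sample size, visits and efficacy analyses do not change.
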